### **Focal Child assessments.**

**Pilot Study:** We examine focal children's language skills. For language skills, we use the teacher DPP and PLRS and parent report DPP at pre- during week one of the pilot.

**Main Study:** We examine focal children's social, behavioral, and language skills as potential mediated outcomes. Measures are administered at three time-points—fall, winter, and spring—of the academic year. All measures are administered using tablet-based devices for efficiency and real-time data processing. For social and behavioral skills, we use the teacher-report Teacher-Child Rating Scale (TCRS (Hightower et al., 1986)), a 32-item teacher-report instrument that captures children's social, behavioral, and emotional competence. For the proposed study, we will use the behavior control items to assess children's problem behaviors and the social competence items to capture three areas of interest: task orientation, assertiveness, and peer social skills. Teachers respond to statements on a 5-point scale (1 = strongly disagree, 5 = strongly agree) to describe each child in relation to these descriptions. This tool is easy and inexpensive to administer and yields psychometrically valid outputs on children's social and behavior issues that are applicable to children with disabilities in inclusive classrooms (Juvonen

& Bear, 1992). For language skills, we use the Developmental Pragmatic Profile (DPP) (Wiig et al., 2004), which is administered on each child in the classroom in the fall and spring (in accordance with the approved/signed informed consent materials), but to focal children again in winter. We examine change on each of three sub-scales: nonverbal skills; conversational skills; and asking for, giving, and responding to information. Teachers rate the child linguistic-pragmatic skills on a 4-point scale for each of 26 items. Also, we administer one subtest of the Preschool Language Screener-5 Assessment: expressive language (Zimmerman et al., 2011). We will explore avenues for data reduction, including use of a latent-variable modeling strategy. The benefit of using this measure is that we have used it in extensive prior studies of similar samples and contexts, thus permitting us to explore study findings in relation to considerably larger samples of children with LI (Justice et al., 2014a) and their approximate annual language growth.

### **Descriptives and possible covariates**

Pilot: Teachers: Teachers will complete a survey prior to the pilot and provide demographics. The survey will also include the peer matrix and 5 questions about past social supports and experience with peer-mediated interventions. During week 6 of the pilot, teachers will complete an 8 item questionnaire to provide information on the feasibility and tolerance of implementing the pilot intervention in their classrooms; Parents: will complete an IFQ with their consent form to determine eligibility. Caregivers of peers and target children will be asked to complete one survey during the pilot, which will collect the following information: demographics, household socioeconomic status (caregiver education levels), a set of 5 items to capture child social network information; the DPP. Only focal child and peer parents who will complete the survey during the pilot.

Peer and target children will be asked to complete a brief 4 minute interview during weeks 1 and 6 of the pilot.

Main Study: Descriptives and potential covariates to be captured and explored in analyses include (1) classmates' language skills (fall and spring DPP completed for each child by teacher), (2) classroom composition characteristics including percentage of children with disabilities, gender, and age (provided by teachers in fall), and (3) focal child sociodemographic factors. For the latter, we collect a questionnaire from the primary caregiver in the fall and spring (in accordance with the approved/signed informed consent materials) to assess household socioeconomic status (caregiver education levels and employment status, household composition, and transience—including whether or not the family experienced a serious family event over the last school year to be answered in spring), home literacy activities per established protocols (Justice, Logan, Işitan, & Saçkes, 2016), and child language history.

#### **e. Confidentiality of Data**

Any data collected will be de-identified to maintain confidentiality. Any participants will be assigned a subject ID. Subject IDs and names will be separated. All data will be stored in a locked cabinet. Audio, proximity, activity, observation and questionnaire record data will be downloaded to a password-protected computer. Only study personnel will have access to this data. Segments of audio, proximity, and activity data will be processed in the cloud using OSU-

configured cloud-computing service, which provide in-transit and in-use encryption of data. OSU will serve as the central data hub and the IRB of record for all study activities.

#### **f. Internal Validity**

Standardized procedures of all instrumentation will be utilized to ensure proper administration

#### **g. Data Analysis**

Aim 1 investigates the effects of peer-mediated PRT on the peer interactions and social status (indicated by individual centrality) within the classroom social network for children with LI. We assess this aim based on 6 to 24 repeated measurements for each outcome variable using multilevel growth models (Raudenbush & Bryk, 2002) to investigate changes in key outcomes over the school year and to accommodate the wait-list experimental design. Longitudinal measurements will be nested within participants and predicted by the time of measurement as well as time-specific intervention status. We include interaction terms between time of measurement and intervention status so that any accelerating or decelerating effects of intervention can be captured. In all models, we control for relevant covariates to increase precision of parameter estimates and power (Hox, Moerbeek, & Van de Schoot, 2010; Raudenbush, Martinez, & Spybrook, 2007). To assess treatment effects on peer interactions, we use the number of peer interaction, number of appropriate peer play, and duration of peer talk for the focal children as the outcome variables in the growth models. Depending on the distribution of the variables, appropriate linear or generalized linear models (e.g., Poisson) will be fitted. To examine treatment effects on social status, we compare the trajectories of individual centrality for the focal children and their classmates, controlling for classroom-level variation. Specifically, intervention effects are tested on key components of the trajectories, such as intercept, linear slope and quadratic slope (i.e., the slowing or acceleration of growth). The growth curves for different groups (treatment, wait-list control, and peer) can then be estimated. Aim 2 determines the extent to which peer-mediated PRT contributes to focal children's social, behavioral, and linguistic skills via the mediation of improved socialization experiences. For this aim, we employ multivariate latent growth models, where latent growth curves of socialization indices and child skills can be modelled simultaneously and the relationships between latent growth parameters examined. In particular, two latent slopes (fall and spring) will be specified for the socialization growth curve to capture the differential growth rate with and without intervention; intervention status will be used as a predictor of the two socialization slopes. Due to the sample size limitation, we will examine one socialization index and one skill variable at a time. We will focus on the following pathways: (a) effect of intervention on focal children's socialization experiences at fall, winter, and spring; and (b) effects of socialization experiences on child skills at fall, winter, and spring. Paths (a)\*(b) allow us to test the indirect effects of PRT on social, behavioral, and linguistic skills. To estimate the mediation effect, we use the product-of-coefficient approach (MacKinnon, Lockwood, Hoffman, West, & Sheets, 2002) with a bootstrapping procedure (Preacher & Hayes, 2004, 2008). This method does not require the assumption of normality for the sampling distribution of the product-of-coefficient. Finally, Aim 3 examines changes in classroom social network dynamics over the school year, and tests the effects of peer-mediated PRT on peer socialization at the classroom level. To address this aim,

we adopt multilevel growth models similar to those described in Aim 1, except with classroom-level social network indices as outcomes and classrooms as the level-2 unit of analysis. With repeated measurements across the school year, the change rates in socialization indices can be estimated for and compared between the intervention period and control period.

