**Main Study:** As a proximal treatment outcome, we examine focal children’s social interactions with classmates in terms of peer interactions and peer talk. These activities are conducted on the same day as the researcher observations and occur 8-16 times annually (three at least 3 during intervention). For peer interactions, we observe the peer interactions of the focal children during observations conducted over the academic year using an established protocol (Brock et al., 2018). These are conducted on the same day as the prior observation (researcher observation), with order randomized. For this observation, observers will observe the focal child for 30 minutes during center time and apply a partial interval recording system involving 15 s of observation and 15 s of documentation. Two variables are captured: (1) peer interactions and (2) play interactions. For peer interactions, each interval is coded for whether nonverbal or verbal interaction was directed to or from the focal child. These simply capture the extent to which focal children interact with peers in the classroom. For play interaction, each interval is coded for four possible categories of play: appropriate peer play, appropriate solitary play, inappropriate play, and no play. These observational data are derived to represent the percentage of intervals in

which behaviors are coded. Reliability estimates are assessed for 20% of observations via double-coding with observers blind to classroom and child condition.

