**Peer Talk:** For peer talk, we will record the amount of incoming and outgoing talk focal children experience using a hands-free voice-activated recorder worn by each child in the vest, with audio capture transcending the entire classroom day. Teachers follow a protocol for placing the vest on each child at the start and end of the day. With multiple hours of audio recorded per child, we will process these recordings to capture duration of outgoing/incoming talk with proximate peers using the following process: (i) augment the voice-recorder ability/voice detection/processing algorithms from the Matlab Audio Systems Toolbox to determine if people are speaking, and how long they are speaking; and (ii) use 2D-proximity data from continuous location tracking to parse the audio tracks across time into the cases where there is simultaneous peer proximity and recorded voice (i.e., peer-to-peer talk for some duration of time that we can obtain from stamp data from proximity/audio recording). While our initial plan does not involve transcribing or otherwise capturing the quality of peer talk, we will pursue additional funds to analyze these audio data later.

**Activity: Main Study Only:** The children's and teacher's vest will also house a small accelerometer as a motion sensor. The output of this sensor will be used to detect classroom activities such as running, sitting, and sleeping.

The audio, proximity, and activity data will be processed using machine learning algorithms that will perform speech annotation, speaker diarization and analyzed for word count estimates, automatic transcriptions, sentiment analysis, and classification of the nature of the interactions, including automatic identification of child-directed speech. Some of these programs require pre-trained machine-learning models housed in the OSU-configured cloud-computing provider Amazon Web Services (AWS), i.e., the computations are carried out in AWS servers, while the data remains accessible only to OSU project staff.

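### Aim 1 models counts and total talk minutes without a denominator, although the focal-child interaction and play measures are defined as percentages of intervals; the gap matters most for peer talk

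*Combined protocol and SAP*

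**What the plan says.** Section III.d (Focal Child observations, Main Study) sets the observation scheme: "observers will observe the focal child for 30 minutes during center time and apply a partial interval recording system involving 15 s of observation", with a further 15 s to document. Each interval is scored for whether any interaction went to or from the focal child. For play, "each interval is coded for four possible categories of play", of which appropriate peer play is one. The section then fixes the scale: "These observational data are derived to represent the percentage of intervals in" which the behaviour was coded. The pilot text uses the same percentage definition.

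Section III.g (Data Analysis, Aim 1) names the outcomes differently: "we use the number of peer interaction, number of appropriate peer play, and duration of peer talk for the focal children". On the model it says that, depending on the distributions, "appropriate linear or generalized linear models (e.g., Poisson) will be fitted".

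The Peer Talk paragraph has audio run across the whole classroom day and keeps only time when recorded voice and peer proximity occur together. On wear time it says "Teachers follow a protocol for placing the vest on each child at the start and end of the day". The Location tracking section gives a nominal six-hour tracking period per observation day.

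No section states an offset, a minimum valid session or recording time, or a rule for short sessions. The relevant covariates in III.g are justified by precision and power, and the covariates listed under Descriptives and possible covariates do not include observed or recorded time.

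**The concern.** The measures and analysis sections give different scales for the same two outcomes, and the third outcome is a total with no denominator in either place. An analyst following III.g literally would model interval counts and summed minutes, so a child with less usable observation or recording would appear less social. If usable time varies at random, this adds noise. If it differs by condition, by time of year or by site, it shifts the intercepts and slopes on which Aim 1 tests the intervention effect. Leaving the scale open also allows the choice to be made after the data are seen.

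The interaction and play outcomes are also not open counts. They are numbers of intervals scored yes, with a ceiling at the number of intervals observed, so Poisson is not a natural example for them.

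**Working it through.** The plan gives no figure to reproduce here. The check is direct arithmetic on the documented session design, with assumed shortfalls labelled as such.

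**Interaction and play**

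- Intervals in a full session: 30 min × 60 / (15 s + 15 s) = 60.
- Count against percentage in a full session: count = 60 × percentage / 100 = 0.6 × percentage. The two scales carry the same information when every session is complete.
- Expected count with *k* intervals observed and occurrence *p*: *k* × *p*. Take *p* = 0.4 (assumed):

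| Minutes observed (below 30: assumed) | Intervals | Expected count | Percentage | Count relative to full session |
|---|---|---|---|---|
| 30 | 60 | 24 | 40% | 1.00 |
| 25 | 50 | 20 | 40% | 0.83 |
| 20 | 40 | 16 | 40% | 0.67 |
| 15 | 30 | 12 | 40% | 0.50 |

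If mean observed time were 30 min in one group and 27 in another (assumed), an unadjusted count model would show 30/27 = 1.11 with no true difference.

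**Peer talk**

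Expected minutes = rate × valid joint hours. At an assumed 10 min per hour, 6, 5, 4 and 3 valid hours give 60, 50, 40 and 30 minutes. Six against five hours gives 60/50 = 1.20 with no true effect. The rate stays at 10 min per hour throughout.

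**Distribution of the interval outcomes**

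If the 60 intervals were independent, the within-session variance would be binomial, 60*p*(1 − *p*), against 60*p* under Poisson. The SD ratio is 1/√(1 − *p*):

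| *p* | Binomial variance | Poisson variance | SD ratio |
|---|---|---|---|
| 0.2 | 9.6 | 12 | 1.12 |
| 0.4 | 14.4 | 24 | 1.29 |
| 0.6 | 14.4 | 36 | 1.58 |

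These ratios depend on independence. With an assumed lag-1 correlation of 0.4, the variance inflation is about (1 + 0.4)/(1 − 0.4) = 2.33. At *p* = 0.4 the variance becomes about 14.4 × 2.33 = 34, above the Poisson 24, so the direction reverses. What holds in either case is the ceiling at the number of intervals observed. The variance has to be estimated, which is why overdispersion should be allowed.

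**The case against.** The best reply is that this is loose wording. The measures section already supplies a denominator for two of the three outcomes, and the word number in III.g may be shorthand for the derived percentage. III.g does not exclude an offset or an exposure covariate. Poisson is only an example within a family chosen by distribution, which leaves room for a binomial model. For talk, the six-hour tracking period and the vest protocol give a common nominal window, and total daily talk is a defensible target. All of this is fair. It lowers the seriousness of the point, but it does not say which scale applies or how valid time enters the talk model.

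A reader might go further and infer that observation time is bound to vary because two sessions compete for center time: "These are conducted on the same day as the prior observation (researcher observation), with order randomized". The roster session takes children × 0.5 min × 4 cycles + 3 × 5 min of breaks. With 495/30 = 16.5 children that is 48 min, over the stated 40 or so. But the Research Design section also gives 900 children in 90 classrooms, or 10 each, which takes 35 min, and 770/90 = 8.6 each, which takes about 32 min. The result turns on which class size is used. The length of center time is not stated, so truncation does not follow even at 48 min.

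A reader might also infer that the Aim 1 comparison is biased. That would need observed or recorded time to differ by condition, season or site, and no such difference is documented.

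**Conclusion.** The point holds as an inconsistency with a missing denominator, and it should be settled before analysis. It is strongest for peer talk, where total minutes are proportional to valid joint recording time and that time is not fixed by the documents; the 1.20 ratio rests on an assumed 6 against 5 hours. For interaction and play it is conditional. The scales are equivalent in complete 60-interval sessions and diverge only when a session is shortened or intervals are lost, at a rate the documents do not give; 16 instead of 24 is an assumed example.

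The documents do not support saying that exposure will vary, that the treatment comparison is biased, or that Poisson errors are too large by a known amount. A bounded yes/no interval outcome is nevertheless better served by a binomial model than by the Poisson example.

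**What to change.** In III.g, replace the two number outcomes with the measure already defined under Focal Child observations: intervals coded out of intervals actually observed. Fit these with a binomial (logit) growth model that allows overdispersion, and remove Poisson as the example for them. Define the talk outcome as minutes per hour of valid simultaneous audio and location recording, or keep minutes in a log-link model with log valid hours as an offset. State how sessions with little valid time are handled.

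The cost is a change of analysis wording. The interval records and the audio and proximity time stamps should supply the denominators, so no new collection is needed. The small downside is that results are reported as a proportion or rate. If a daily total is wanted for readers, the fitted rate can be scaled to the nominal six-hour period.

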The study uses a wait-list **experimental design** to estimate treatment impacts, with 30 Ohio classrooms assigned to the treatment condition and 20 to the control condition. All remaining 40 classrooms will be recruited by our partners at external sites and serve control condition classrooms. Within each classroom, the focal participants are 30 children with LI, one selected per classroom using a priori exclusionary and inclusionary criteria. The wait-list design allows eligible children with LI in control classrooms to receive treatment in the spring semester; this also allows for ongoing evaluation of changes in socialization processes in treatment classrooms through spring. Study methods with OSU classrooms use a sequential cohort design, with 15 classrooms participating in each of two consecutive years to disperse study activities over a 24-month period. Classrooms will be recruited via our extensive network of affiliated preschool programs across the state of Ohio, with eligible classrooms utilizing a 50/50 inclusive service delivery model (50% of children with disabilities). In the fall of each year, once all 15 classrooms are recruited, simple random assignment will be used to allocate 10 classrooms to the treatment group and 5 to the control group, with the latter implementing intervention in spring per the wait-list design. In addition, our colleagues at the University of Kansas, are employing similar observation methods. We will thus incorporate 20 classrooms (University of Kansas) to serve as control condition classrooms, allowing for a more robust sample of natural conditions in preschool classrooms across contexts.

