### **d. Measures and Instrumentation**

**Researcher observations.** Researcher observations of peer social interactions are adapted from a validated observation protocol (Schaefer, Light, Fabes, Hanish, & Martin, 2010).

Pilot Study: Using trained, reliable observers blind to study hypotheses and classroom study condition, a ~40-min observation session will be conducted in each classroom once per week during weeks 2-6 of the pilot. The observer will observe the classroom during center time and use the list of peer and focal children to structure four partial interval observation cycles; in each cycle, the observer observes each child for 15 s followed by 15 s recording and then moves to the next child. At the end of one cycle, the observer takes a 5-min break. When observed, each child is recorded for any interaction partners (up to five) based on presence of a verbal or physical exchange or parallel play in the same activity during the 15-s observation. Reliability estimates will be assessed for 10% of cycles via double-coding. Based on researcher

observations, a social network will be created for each classroom per observation window. It will be stored in a symmetric square matrix, where the rows and columns represent the classroom roster and each cell value refers to the frequency at which the pair of children play with each other.

Main Study: Using trained, reliable observers blind to study hypotheses and classroom study condition, a ~40-min observation session will be conducted in each classroom 8-16 times over the academic year. The observer will observe the classroom during center time and use a randomized list of children to structure four partial interval observation cycles; in each cycle, the observer observes each child for 15 s followed by 15 s recording and then moves to the next child. At the end of one cycle, the observer takes a 5-min break. When observed, each child is recorded for any interaction partners (up to five) based on presence of a verbal or physical exchange or parallel play in the same activity during the 15-s observation. Reliability estimates will be assessed for 10% of cycles via double-coding. Based on researcher observations, a social network will be created for each classroom per observation window. It will be stored in a symmetric square matrix, where the rows and columns represent the classroom roster and each cell value refers to the frequency at which the pair of children play with each other.

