For the proposed study, researcher observations are executed on days these location recordings occur, so that we can not only triangulate the social network data, but also validate that social networks based on location tracking validly represent authentic forms of peer socialization. Based on each social network generated from either researcher observation or location tracking across the 8-16 timepoints, the social status of each child in the classroom network will be represented by two types of individual centrality indices: degree centrality (i.e., the amount of social interactions directly associated with a child) and eigenvector centrality (i.e., the amount of social interactions directly associated with a child and indirectly associated with the child through their peers, e.g., “friends’ friends”). Classroom network density is also calculated to represent the average interaction intensity in the classroom, with higher values representing a more closely connected classroom network.

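### Centrality scores from one session share a symmetric matrix, and the Aim 1 social-status model states no term that clearly covers the resulting dependence

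*Combined protocol and SAP*

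**What the plan says.** Section III.d (Researcher observations, Main Study) says that "a social network will be created for each classroom per observation window", and of that network: "It will be stored in a symmetric square matrix, where the rows and columns represent the classroom roster". The location-tracking data likewise give one classroom network per window. Two indices are then computed for each child from each network. One is degree centrality, which totals a child's own direct contacts. The other is eigenvector centrality, which also counts contacts reached through classmates.

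Section III.g sets out the Aim 1 growth model: "Longitudinal measurements will be nested within participants and predicted by the time of measurement as well as time-specific intervention status". For social status it adds: "we compare the trajectories of individual centrality for the focal children and their classmates, controlling for classroom-level variation". It continues: "The growth curves for different groups (treatment, wait-list control, and peer) can then be estimated".

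The plan names no classroom-by-session effect, no dyadic or network covariance, no robust variance and no permutation test. It does not say what form the classroom adjustment takes, whether intervention status is attached to the classroom or to the focal child, or how eigenvector centrality is scaled.

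**The concern.** In a symmetric matrix the cell for children i and j adds to the degree of both. Two children's scores from the same session therefore move together even when every tie varies independently. Shared conditions on the day, such as activity, attendance and observer, would add to this. Child effects and an ordinary classroom intercept or slope absorb what is stable or trending over the year. They do not absorb what is particular to one session.

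The consequence depends on the contrast. If status takes the same value for every child in a classroom-session, the unmodelled correlation falls directly on the status coefficient, and effects on classmates or on the class look too precise. In a within-classroom contrast the shared part should cancel but is counted as noise, so focal-minus-classmate looks too imprecise.

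The plan could also contradict itself. For a fixed roster, network density is mean degree rescaled, and Aim 3 analyses it with the classroom as the level-2 unit. A class-wide status effect from the Aim 1 rows would use nearly the same information and could report a clearly smaller standard error.

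**Working it through.** The documents give no sample-size calculation, alpha, SD, intraclass correlation or standard error, so there is no stated figure to reproduce.

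**Inputs from the documents.** The roster size n is not consistent: 495/30 = 16.5 (section III.b; 16 used), 900/90 = 10, or 770/90 = 8.6 (section III.a; 9 used). Sessions number 8–16 in section III.d and 6–24 in section III.g. Each cohort is to "allocate 10 classrooms to the treatment group and 5 to the control group". Two cohorts give 20:10, the split used here, although section III.a also gives 30 treatment and 20 control Ohio classrooms. There is one focal child per classroom.

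**Step 1: shared cells alone, degree centrality.** Assume independent ties with equal variance s².
- Var(degree) = (n−1)s² and Cov(two children's degrees) = s², so r = 1/(n−1): 0.125 at n = 9, 0.111 at n = 10, 0.067 at n = 16. Simulated Poisson matrices gave 0.127, 0.113 and 0.065.
- Variance of the session mean = 4·[n(n−1)/2]s²/n² = 2(n−1)s²/n, against (n−1)s²/n if rows were independent. The ratio is 2 for any n.
- Model SE / true SE = 1/√2 = 0.71. A nominal 5% test rejects 2[1−Φ(1.96/√2)] = 16.6%.

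**Step 2: by contrast, whole-classroom status coding.**
- Classmates (n−1 children): the variance factor is 1+(n−2)r. At n = 9 it is 1+7/8 = 1.875, SE ratio 1/√1.875 = 0.73. At n = 16 it is 1+14/15 = 1.933, SE ratio 0.72.
- Focal minus classmates: the SE ratio is 1/√(1−r). At n = 9, 1/√0.875 = 1.07. At n = 16, 1/√0.933 = 1.03.

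**Step 3: growth-model check.** Model-based and sandwich standard errors were compared for a growth model with child and classroom random intercepts, with and without slopes. It used 20:10 classrooms, 8 sessions and rosters of 9 and 16. Assumed values: child variance 1, classroom variance 0.3, residual variance 1, the sessions at which intervention starts, and a shared session shock of 0, 10% or 30% of residual variance. Entries are model SE / true SE, with the rejection rate of a 5% test in brackets.

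| Contrast | No shock | 10% shock | 30% shock |
|---|---|---|---|
| Status effect, classmates | 0.72–0.73 (15–16%) | 0.56–0.64 (21–28%) | 0.41–0.52 (31–42%) |
| Status effect, class average | 0.71 (16–17%) | 0.54–0.61 (23–29%) | 0.40–0.49 (33–43%) |
| Focal minus classmates | 1.03–1.07 (3.6–4.3%) | 1.09–1.12 (2.8–3.3%) | 1.22–1.27 (1.3–1.7%) |
| Focal only | 1.00 (5.0–5.1%) | 0.99–1.00 (5.1–5.2%) | 0.98–0.99 (5.1–5.5%) |

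With 16 sessions (n = 16, no shock) the ratios are unchanged. Adding a classroom-by-session random effect brings every ratio in the table to 1.00.

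**Step 4: status coded on focal children only.** With 12 sessions, rosters of 9 and 16 and the same variances and shocks, the SE ratio is 1.00 and rejection is 5.0% throughout. A classroom-by-session effect still lowers the standard error, by 2–3% from shared cells alone and by 12–14% with a 30% shock.

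**Step 5: eigenvector centrality.** Under unit-norm scaling the squared scores sum to a constant, so one child's rise is others' fall. Simulated same-session correlations were negative, about −0.04 to −0.12 over rosters of 9 to 20. Under maximum scaling they were slightly positive (+0.02 at n = 9, +0.07 at n = 16). A run at r = −0.05 (n = 16) gave ratios of 1.78 for classmates, 0.98 for focal minus classmates and 1.00 for focal only, so the directions reverse. The session random effect left these ratios unchanged, because a variance component cannot represent a negative correlation.

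**The case against.** The strongest reply is that the plan does not state the model being criticised. It never says that scores are independent given child and classroom, and a classroom-by-session term could fall under its general reference to classroom-level variation. Nor does it say that status is shared by the whole classroom. Section III.c has focal children receiving the intervention, and section III.g lists a single peer group, which fits coding on focal children. Under that coding the inflation disappears. This stands: the defect is an unspecified covariance structure and coding, not a stated wrong model.

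A second reply is that the Aim 1 target is children with language impairment, one focal child per classroom, and that effect is almost untouched. The class-wide question belongs to Aim 3, which already uses the classroom as its unit. This also stands, and it limits the consequence. But section III.g makes the focal-versus-classmate comparison its social-status analysis and promises a peer curve, so affected contrasts will be reported.

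A third reply is that the exact doubling needs independent, equal-variance ties, which the 15-second intervals and the cap of five partners make an idealisation. That is fair; the figures are a benchmark.

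A reader might infer that false-positive rates of 20–40% are to be expected, or that every centrality result will be too precise. The documents support neither. The higher rates need session shocks whose size is not given, and the direction differs by contrast, by status coding and by eigenvector scaling.

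**Conclusion.** The point holds in a limited form. The dependence follows from the documented symmetric matrix, and no stated term clearly covers it. For degree centrality, with whole-classroom status coding and independent, equal-variance ties, the status effect on classmates or the class has a standard error 27–29% too small (about 15–17% rejection at a nominal 5%). The focal-minus-classmate standard error is 3–7% too large. Shared session shocks would enlarge both errors by an unknown amount.

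The focal-only treatment effect is nearly unaffected. If status is coded on focal children only, the test is valid and the cost is some lost precision. For eigenvector centrality the size and direction cannot be settled until the scaling is stated, and under unit-norm scaling the directions reverse.

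It would go too far to conclude that the plan commits to a wrong model or that the main focal-child result is invalid. The plan should nevertheless be changed, because the remedy is cheap and helps under either coding.

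**What to change.** In the Aim 1 social-status models of section III.g:

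1. Add a classroom-by-session random effect (one per matrix) for degree centrality, for both the observation and the location networks.
2. For both centrality indices, base inference on classroom-clustered small-sample standard errors, or on re-randomisation limited to the classrooms that were actually randomised. The externally recruited control classrooms were not randomised and cannot be permuted. For eigenvector centrality this step is essential, since the random effect cannot represent a negative correlation; its scaling should also be stated.
3. State how intervention status is coded (whole classroom or focal child) and which contrast is the treatment effect.

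The cost is slightly more analysis work and wider intervals for classmate or class-wide effects. No new data are needed.
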